## PET/CT IMAGING PROCESSING GUIDELINES

Overview: When the PET/CT is ordered as a clinical workup, a diagnostic report will be issued by the Nuclear Medicine Department faculty. Neither [name] nor [name] will participate in the preparation or issuing of this report.

Methodology of SUV Evaluation: Anonymized FDG PET/CT data from CNDA will be uploaded into a MIM workstation (MIM Software Inc., Cleveland, Ohio). Fused MPRAGE/DWI images will be used. The region of interest chosen for the evaluation of ADC values will be copied onto the FDG CT/PET, and the SUVmax will be measured. While there is significant variability in SUV measurements [Kinehan, 2010], the reported literature suggest SUVmax > 9.0 -with interquartile range (IQR) 7.4–13.9 and range of 1.5-20.1 - is diagnostic of squamous cell carcinoma [Schwartz, 2004; Morand, 2018] for the primary mass and >4.5 for nodal tumor [Paidpally, 2012]. PET/CT studies are standard of care and are reported as clinical studies.

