## 2.0 OBJECTIVES

The Specific Aim of this application is as follows: To compare SUVmax and ADCmean/min values to assess the capability of the new DWI pulse sequence to differentiate post-treatment change from residual or early recurrent tumor.

Hypothesis: The optimized research DWI pulse sequence obtained up to 3 weeks post treatment will accurately identify residual/recurrent tumor, as confirmed by the clinical FDG PET/CT obtained at 3-6 months. This would potentially result in a modification of imaging follow-up algorithms, increased cost-savings and eliminate radiation exposure to patients inherent in PET/CT. This would also result in earlier changes to treatment regimens and stratify patients into more or less aggressive tumor response to treatment. The gold-standard will be histological tissue where available and/or 1-year clinical and imaging outcomes, including imaging outcome measurements such as RECIST 1.1 [De Bree, 2017], PERCIST [Joo Hyun, 2016] and iRECIST [Persigehl, 2020].

**Figure 1:** DWI data obtained from a healthy volunteer with a GE 3 Tesla system and eight-channel neurovascular array coil. Single-shot EPI-based DWI was obtained: matrix size = 128  $\times$  128; parallel imaging acceleration factor = 2; field of view = 24 cm  $\times$  24 cm; b-value = 1000 s/mm^2. B, High-resolution DWI data obtained with four-shot interleaved EPI pulse sequence (matrix size = 256  $\times$  256; field of view = 24 cm  $\times$  24 cm; b-value = 1000 s/mm^2) and reconstructed with our developed MUSE algorithm.

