## **MRI PROCESSING GUIDELINES**

**Overview:** All MRI studies will be blindly evaluated by at least two experienced neuroradiologists (Drs. [name] and [name]). If there is an urgent or emergent finding obtained by the research MRI study, this will be communicated by one of the neuroradiologists directly to the ENT physician for follow up who is caring for the patient, as per normal departmental protocol. In the case of this study, incidental findings are defined as anything not already noted in the medical record.

**Methodology of MRI Evaluation:** The research MRI study of the head and neck will be performed on a Siemens 3T MRI Scanner system located in the Center for Clinical Imaging Research (CCIR). Multiplanar / multisequence MRI data including the optimized research DWI sequence will be acquired. MRI subjects must complete an MRI screening evaluation form before entering MRI zone 3 or the scanning room. Images will be anonymized and sent to CNDA for archiving after diagnostic reports are complete. All anonymized MRI studies will then be blindly evaluated by at least two experienced neuroradiologists (Drs. [name] and [name]). MUSE image processing will be applied post-acquisition.

**Methodology of ADC Evaluation:** The primary tumor, suspicious lesion, and/or area of post-treatment change will be first identified in the anatomical images and then outlined in the ADC sequence by experienced neuroradiologists (Drs. [name] and [name]), excluding areas of cystic change and necrosis. If there are multiple lesions, only the dominant lesion with the lowest ADC will be utilized for analysis, akin to RECIST criteria. If there is geometric distortion, a region of interest will be placed in the undistorted region only. A histogram analysis method will be used to examine the distribution of ADC values within each region of interest (ROI). Only measurable disease defined as a primary tumor, a suspicious lesion, and/or an area of post-treatment change measuring at least 0.5 cm in two perpendicular dimensions will be used. Technically poor or non-diagnostic MR images will be excluded. ADCmean/min will be computed.

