## 7.0 STATISTICAL CONSIDERATION

### STATISTICAL ANALYSIS

Study Design and Endpoints: This is a pilot study designed as a paired, prospective, single-blinded study in which we compare the sensitivity and specificity of the optimized DWI sequence ADCmean/min versus FDG PET/CT SUVmax for the evaluation of recurrent SCC in post-treatment patients. The primary endpoints of sensitivity and specificity will evaluate the diagnostic accuracy of the optimized DWI sequence ADCmean/min versus the standard-of-care FDG PET/CT SUVmax. The secondary endpoint will evaluate if the enhanced DWI sequence can more expediently assess non-responders to treatment as compared to FDG PET/CT.

Aim 1: The 60 subject sample size for this pilot study was chosen for feasibility of recruitment based on the approximately 650 PET/CT exams performed for head and neck tumor in 2018. ROI will be used for statistical assessments of ADC measurements (see methodology of ADC measurement, above). FDG-PET SUVmax results will be used as the reference standard for tumor or non-tumor tissue. ADCmean, ADCmin and standard deviation will be used to describe distribution of ADC measurements (AADC) in tumor and non-tumor tissues and independent sample t-test will be used to compare ADC measurements between the two groups. Mean difference and 95% confidence interval around that will be used to interpret our results. For ROC analysis, the area under the curve (AUC) will be calculated and the Youden's J index will be used to identify the value of the predictor variable that optimized sensitivity and specificity. Youden's J index varies from 0-1. The threshold value that provides the value of the J index closer to 1 is the value with the best performance and discriminative power. PPV and NPV will also be evaluated. The logistic regression model allows for evaluating this impact after controlling for potential confounders. We will explore the linearity assumption of relationship of delta ADC with logit of outcome (response to treatment) and if the assumption is violated,

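### SUVmax is read only in the ROI copied from the earlier MRI, which suits a lesion-level comparison but not a per-patient one, and the plan does not state its unit of analysis

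*Combined protocol and SAP*

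**What the plan says.** **Where SUVmax comes from.** The PET/CT Imaging Processing Guidelines state: "The region of interest chosen for the evaluation of ADC values will be copied onto the FDG CT/PET, and the SUVmax will be measured". No other SUVmax measurement is described. The same section says that for the clinical PET/CT "a diagnostic report will be issued by the Nuclear Medicine Department faculty", but no part of the plan turns that report into the PET test result.

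**How the ROI is drawn.** Under the MRI Processing Guidelines the ROI may cover primary tumor, a suspicious lesion or treatment-related change. It leaves out cystic and necrotic areas. Three further limits apply:
- one lesion only: "If there are multiple lesions, only the dominant lesion with the lowest ADC will be utilized for analysis";
- tissue free of distortion: "If there is geometric distortion, a region of interest will be placed in the undistorted region only";
- a minimum size, since only disease "measuring at least 0.5 cm in two perpendicular dimensions will be used".

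**Timing.** Section 4.0 places the MRI within 3 weeks after treatment and the PET/CT at 3 to 6 months.

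**Unit and reference.** Section 7.0 compares the sensitivity and specificity of ADC and SUVmax "for the evaluation of recurrent SCC in post-treatment patients", which reads as per patient. Its Aim 1 paragraph says "FDG-PET SUVmax results will be used as the reference standard for tumor or non-tumor tissue", which reads as per tissue or lesion. Section 2.0 names a different reference: "The gold-standard will be histological tissue where available and/or 1-year clinical and imaging outcomes".

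**The concern.** The index test decides where its comparator may look. A new node, or a lesion other than the one with the lowest ADC, may be plainly visible on PET/CT and still leave SUVmax in the copied ROI below any cut-off.

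Whether this matters depends on the unit. For the question of how ADC and SUV compare in the same tissue, reading both in one place is sound. For the question of whether early DWI finds recurrence in a patient as well as PET/CT does, PET has been stopped from showing what it can find. Section 2.0 hopes to change imaging follow-up and spare patients PET/CT radiation, and those are patient-level conclusions. On sensitivity the restriction favours DWI. On specificity it may favour PET, because inflammatory uptake elsewhere, which Section 1.0 names as a cause of PET false positives, is left out too.

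**Working it through.** The plan has no figure to reproduce: the sample of 60 was chosen for feasibility, with no power calculation. The check traces the definitions and then illustrates the size.

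**1. Age of the ROI at PET/CT.** Taking 3 to 6 months as 13 to 26 weeks, and the MRI at 0 to 3 weeks, the gap runs from 13 - 3 = 10 to 26 - 0 = 26 weeks.

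**2. Tumor wholly outside the ROI, by unit and reference.**
- *Lesion level:* the tissue in the ROI contains no tumor and is correctly labelled non-tumor. The outside tumor is not an observation. There is no error.
- *Per patient, SUVmax as reference (Section 7.0):* the patient is labelled non-tumor, so a DWI miss there disappears. SUVmax is also the comparator, and at one cut-off it agrees with itself by construction.
- *Per patient, histology or one-year outcome as reference (Section 2.0):* the patient is a true recurrence and PET is scored as a miss, unless the ROI happens to read positive.

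**3. PET sensitivity against the Section 2.0 reference.** Let P be true per-patient PET sensitivity, f the share of recurrences wholly outside the ROI, and q the chance that a tumor-free ROI reads PET-positive. Then:
- ROI-limited PET sensitivity = (1 - f)P + fq
- Shortfall = P - [(1 - f)P + fq] = f(P - q)

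Assumed, not in the documents: P = 0.90, and q = 0 or 0.15.

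| f | Sensitivity, q = 0 | Shortfall | Sensitivity, q = 0.15 | Shortfall |
|---|---|---|---|---|
| 10% | 0.81 | 0.09 | 0.825 | 0.075 |
| 20% | 0.72 | 0.18 | 0.75 | 0.15 |
| 40% | 0.54 | 0.36 | 0.60 | 0.30 |

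**4. Effect on PET minus DWI.** DWI has one planned reading per patient, with some sensitivity D* that is the same however PET is read. The difference is P - D* with PET located on its own and (1 - f)P + fq - D* with PET limited to the ROI. D* cancels, so the understatement is f(P - q) whatever DWI does with outside tumors.

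**5. Scale against the planned 90% interval.** Assume 18 recurrences among 60, f = 20%, q = 0, DWI sensitivity 0.80 inside the ROI, a 0.20 chance that a tumor-free ROI reads DWI-positive, and independent test results within each group of recurrences (inside or outside the ROI).
- D* = 0.8 × 0.80 + 0.2 × 0.20 = 0.68.
- PET located on its own: d = 0.90 - 0.68 = 0.22. The discordant proportions are 0.288 and 0.068, so the interval is 0.22 ± 1.645 × √[(0.356 - 0.22²)/18], or 0.005 to 0.435.
- PET limited to the ROI: d = 0.72 - 0.68 = 0.04. The discordant proportions are 0.144 and 0.104, so the interval is 0.04 ± 1.645 × √[(0.248 - 0.04²)/18], or -0.15 to 0.23.

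The shift of 0.18 is nearly as large as the half-width of either interval (about 0.19 to 0.22).

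**6. If SUVmax is the reference and a per-patient claim is made.** Use the same inputs, DWI specificity 0.80, and SUVmax labelling ROI tissue without error. Of 18 recurrences, 0.2 × 18 = 3.6 are labelled negative, leaving 14.4. DWI sensitivity appears as 0.80 against a per-patient value of (14.4 × 0.80 + 3.6 × 0.20)/18 = 0.68. NPV appears as 36.48/39.36 = 0.927 against 33.6/39.36 = 0.854.

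**7. Specificity.** If PET specificity inside the ROI is 0.85, and 5% to 15% of patients without recurrence have false-positive uptake elsewhere, per-patient specificity is 0.85 × 0.95 = 0.81 down to 0.85 × 0.85 = 0.72.

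**The case against.** The best defence is that this is a lesion-level study. The Specific Aim compares SUVmax with ADC values, the MRI guidelines keep one dominant lesion, and the Aim 1 paragraph speaks of tissue. On that reading the copied ROI is the right method and what remains is wording. This stands in part. A reader might infer that the plan miscodes every tumor outside the ROI as non-tumor. The documents do not support that at lesion level, and the fault appears only when a per-patient conclusion is drawn. But Section 7.0 also frames its endpoints by patient, and Section 2.0 draws patient-level implications, so the lesion-level reading is not secured.

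A second defence is that the clinical PET/CT is not ignored. Section 2.0 expects it to confirm the DWI finding, and it can reach the reference side through one-year imaging outcomes. So it would be wrong to say that the clinical read has no route into the study. However, Section 2.0 gives no rule that makes the read part of the PET test result.

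Third, the size is not known. The documents give neither f nor the accuracy of either test, and because the ROI may be treatment-related change, f cannot be inferred. This stands. With f = 10% and the other inputs of step 5, both intervals include zero.

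Fourth, a PET result taken from the whole head and neck, set against a single-lesion DWI reading, is itself uneven. This also stands, and is a reason to report both analyses.

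**Conclusion.** The point holds as a limit on what the analysis can claim. SUVmax read only in the copied ROI supports a lesion-level comparison. It does not support a per-patient comparison of DWI with PET/CT, and the plan does not say which it intends. Section 7.0 also uses SUVmax as comparator and reference, in conflict with Section 2.0.

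If a per-patient claim is made against histology or one-year outcome, PET sensitivity and the PET-minus-DWI difference are understated by f(P - q). That is 0.09, 0.18 or 0.36 at f = 10%, 20% or 40% with P = 0.90 and q = 0, and 0.075, 0.15 or 0.30 with q = 0.15. The form of the bias follows from the plan, but its size rests on assumed values. PET specificity may be overstated at the same time, so the documents do not support a reading that the design favours DWI on every measure. Nor do they show that recurrence site goes unrecorded: the list in Section 4.0 has no such item, but it refers to an attached data sheet that is not in the public text.

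**What to change.** 1. State the unit of analysis in Section 7.0. Reconcile Sections 2.0 and 7.0 so that both tests are scored against histology and/or one-year outcome, not against SUVmax.
2. Keep the copied-ROI SUVmax for the lesion-level analysis and limit its conclusions to the ROI. For any per-patient claim, co-report a PET result from the existing Nuclear Medicine report: the most FDG-avid suspicious head-and-neck lesion, or negative if none is named. The DWI result stays the single-ROI reading as planned.
3. Record whether each recurrence lies inside or outside the ROI, if the data sheet does not already do so. Report the per-patient comparison with and without outside-ROI recurrences, since some may have arisen after the MRI.
4. Add a sensitivity analysis restricted to outcomes not determined by the same PET/CT, because the clinical report may influence the outcome.

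**Cost.** One further PET result and at most one further data field per patient, from a scan and report that already exist, plus the added analyses. No new scan, visit or second reader is needed. The drawbacks are that the per-patient comparison is not co-localised, sets a head-and-neck-wide PET read against a single-lesion DWI read, and may show lower PET specificity. In return, the pilot yields an estimate of f for a later trial.

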## 5.0 ADVERSE EVENT MONITORING AND REPORTING

### 5.1 Adverse Events (AEs)

Definition: any unfavorable medical occurrence in a human subject including any abnormal sign, symptom, or disease related to this study protocol. For purposes of this research project, AEs associated with the MRI will be tracked.

Attribution (Relatedness), Expectedness, and Seriousness: the definitions for the terms listed that should be used are those provided by the Department of Health and Human Services' Office for Human Research Protections (OHRP). A copy of this guidance can be found on OHRP's website at: <http://www.hhs.gov/ohrp/policy/advevntguid.html>.

### 5.2 Unanticipated Problems

Unexpected (in terms of nature, severity, or frequency) given (a) the research procedures that are described in the protocol-related documents, such as the IRB approved research protocol and informed consent document; and (b) the characteristics of the subject population being studied;

Related or possibly related to participation in the research (in this guidance document, possibly related means there is a reasonable possibility that the incident, experience, or outcome may have been caused by the procedures involved in the research); and

Suggests that the research places subjects or others at a greater risk of harm (including physical, psychological, economic, or social harm) than was previously known or recognized.

### 5.3 Noncompliance

**Definition:** failure to follow any applicable regulation or institutional policies that govern human subject research or failure to follow the determinations of the IRB. Noncompliance may occur due to lack of knowledge or due to deliberate choice to ignore regulations, institutional policies, or determinations of the IRB.

### 5.4 Serious Noncompliance

**Definition:** noncompliance that materially increases risks, and results in substantial harm to subjects or others, or that materially compromises the rights or welfare of participants.

## **5.5 Protocol Exceptions**

**Definition:** A planned deviation from the approved protocol that are under the research team's control. Exceptions apply only to a single participant or a singular situation. Preapproval of all protocol exceptions must be obtained prior to the event.

## **5.6 Reporting to the Human Research Protection Office (HRPO)**

Reporting will be conducted in accordance with Washington University IRB Policies.

Pre-approval of all protocol exceptions must be obtained prior to implementing the change.

These events must be reported to the IRB within **10 working days** of the occurrence of the event or notification to the PI of the event. The death of a research participant that qualifies as a reportable event should be reported within **1 working day** of the occurrence of the event or notification to the PI of the event.

## **5.7 Reporting to the Quality Assurance and Safety Monitoring Committee (QASMC) at Washington University**

The PI is required to notify the QASMC of any unanticipated problems involving risks to participants occurring at WU or any BJH or SLCH institution that has been reported to and acknowledged by HRPO. (Unanticipated problems reported to HRPO and withdrawn during the review process need not be reported to QASMC.)

QASMC must be notified within **10 days** of receipt of IRB acknowledgment via email [[contact]](mailto:[contact]). Submission to QASMC must include the myIRB form and any supporting documentation sent with the form.

## **5.8 Time Frame for Reporting Required Events**

Any events that require reporting will be submitted per current IRB guidelines.

## **5.9 Incidental Findings**

The research MRI scan is not a clinical MRI examination and is not conducted to diagnose brain abnormalities. However, some of the sequences are similar to clinical tests, and these images are reviewed for incidental findings by a board-certified radiologist. If there is an incidental observation from the testing which may be clinically significant, such as a suspected tumor or aneurysm, the Principal Investigator will communicate this information to the treating physician for review; this includes incidental finding of new tumor. If indicated, the Principal Investigator will contact the participant with this information. With your permission your doctor may also be contacted so that follow-up may occur as appropriate.\*

## **6.0 DATA AND SAFETY MONITORING**

In compliance with the Washington University Institutional Data and Safety Monitoring Plan, the Principal Investigator will provide a Data and Safety Monitoring (DSM) report to Washington University Quality Assurance and Safety Monitoring Committee (QASMC) semi-annually beginning six months after accrual has opened (if at least one patient has been enrolled) or one year after accrual has opened (if no patients have been enrolled at the six-month mark).

The Principal Investigator will review all patient data at least every six months, and provide a semi-annual report to the QASMC. This report will include:

- HRPO protocol number, protocol title, Principal Investigator name, data coordinator name, regulatory coordinator name, and statistician

- Date of initial HRPO approval, date of most recent consent HRPO approval/revision, date of HRPO expiration, date of most recent QA audit, study status, and phase of study
- History of study including summary of substantive amendments; summary of accrual suspensions including start/stop dates and reason; and summary of protocol exceptions, error, or breach of confidentiality including start/stop dates and reason
- Study-wide target accrual and study-wide actual accrual
- Protocol activation date
- Average rate of accrual observed in year 1, year 2, and subsequent years
- Expected accrual end date
- Objectives of protocol with supporting data and list the number of participants who have met each objective
- Early stopping rules with supporting data and list the number of participants who have met the early stopping rules
- Power analysis and/or interim analysis (if described in the protocol)
- Summary of toxicities
- Abstract submissions/publications
- Summary of any recent literature that may affect the safety or ethics of the study

The study principal investigator and Research Patient Coordinator will monitor for serious toxicities on an ongoing basis. Once the principal investigator or Research Patient Coordinator becomes aware of an adverse event, the AE will be reported to the HRPO and QASMC according to institutional guidelines.

## 7.0 STATISTICAL CONSIDERATION

### STATISTICAL ANALYSIS

Study Design and Endpoints: This is a pilot study designed as a paired, prospective, single-blinded study in which we compare the sensitivity and specificity of the optimized DWI sequence ADCmean/min versus FDG PET/CT SUVmax for the evaluation of recurrent SCC in post-treatment patients. The primary endpoints of sensitivity and specificity will evaluate the diagnostic accuracy of the optimized DWI sequence ADCmean/min versus the standard-of-care FDG PET/CT SUVmax. The secondary endpoint will evaluate if the enhanced DWI sequence can more expediently assess non-responders to treatment as compared to FDG PET/CT.

Aim 1: The 60 subject sample size for this pilot study was chosen for feasibility of recruitment based on the approximately 650 PET/CT exams performed for head and neck tumor in 2018. ROI will be used for statistical assessments of ADC measurements (see methodology of ADC measurement, above). FDG-PET SUVmax results will be used as the reference standard for tumor or non-tumor tissue. ADCmean, ADCmin and standard deviation will be used to describe distribution of ADC measurements (AADC) in tumor and non-tumor tissues and independent sample t-test will be used to compare ADC measurements between the two groups. Mean difference and 95% confidence interval around that will be used to interpret our results. For ROC analysis, the area under the curve (AUC) will be calculated and the Youden's J index will be used to identify the value of the predictor variable that optimized sensitivity and specificity. Youden's J index varies from 0-1. The threshold value that provides the value of the J index closer to 1 is the value with the best performance and discriminative power. PPV and NPV will also be evaluated. The logistic regression model allows for evaluating this impact after controlling for potential confounders. We will explore the linearity assumption of relationship of delta ADC with logit of outcome (response to treatment) and if the assumption is violated,

polynomial effects will be explored, and data transformation will be employed as needed. All statistical analysis will be carried out by [name], a biostatistician in the ENT Department with extensive experience in head and neck cancer research. A 90% confidence interval will be calculated for the differences in sensitivity and specificity of the enhanced DWI sequence ADCmean/min as compared with the standard-of-care FDG PET/CT SUVmax. The positive and negative predictive values will also be evaluated. Since this is a pilot study, no existing data can be utilized to calculate a power analysis.

A binary logistic regression model will be utilized to evaluate the impact of the change in ADC in predicting early non-responders to treatment. A p-value will be calculated to evaluate if the enhanced DWI sequence can more expediently identify non-responders to treatment as compared to FDG PET/CT.

(\*\*Note: Patients who do not undergo SOC PET/CT at the 3-6 month time point will be considered inevaluable and will be replaced.)

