## 1.0 BACKGROUND AND RATIONALE

Head and neck tumors can be a significant imaging diagnostic challenge. Anatomic imaging alone is insufficient to differentiate between post-treatment change and recurrent tumor, as both demonstrate increased T2/FLAIR signal and enhancement. Diffusion-weighted sequences (DWI) is a more sensitive and specific sequence that can be used to evaluate this tumor, and that can more easily differentiate between residual/recurrent tumor and post-treatment change (Vandecaveye, 2007). Metabolic imaging with FDG PET/CT is impacted by false-positives in the setting of inflammation or post-radiation necrosis and thus, data must be acquired 8-12 weeks post-treatment to avoid this pitfall. Moreover, PET/CT imaging is less available compared to MRI or CT. MRI does not require ionizing radiation, which is an important factor in head and neck squamous cell cancer patients, as they have an increased risk of secondary tumors such as lung cancer.

MRI systems that include diffusion-weighted imaging (DWI) and apparent diffusion coefficient (ADC) measurements hold promise to facilitate differentiation of tumor recurrence from post-treatment changes and associated complications, since areas of tumor demonstrate restricted diffusion and post-treatment changes do not [Chawla, 2009; Friedrich, 2008; Hermans, 2010; Jansen 2010; King, 2010 and 2013; Maeda, 2008; Mudana, 2018; Perrone, 2011; Vandecaveye, 2007 and 2010]. However, there are multiple pitfalls associated with conventional DWI related to artifacts such as fat saturation, distortion, aliasing/ghosting and spatial resolution. These limit the utility of this technique.

We propose a longitudinal study evaluating post-treatment changes in patients with squamous cell carcinoma (SCC) of the neck using an **innovative optimized DWI pulse sequence to identify more accurately recurrent tumors as well as early non-responders to therapy**.

[figure not shown]

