## **4.0 STUDY PROCEDURES**

### **IMAGING PLAN**

Overview: 60 biopsy-proven neck SCC patients after treatment with surgery, radiation or chemo-radiation will be enrolled for this trial. The Otolaryngology, Head and Neck Surgery physicians and their clinic staff will assist in coordinating enrollment. The patients will undergo an optimized research neck DWI MRI, up to 3 weeks post-treatment and then a standard-of-care 3-6 months post-treatment FDG PET/CT examination. (\*\*Note: Patients who do not undergo SOC PET/CT at the 3-6 month time point will be considered inevaluable and will be replaced.) Patients who sign the consent form but do not have the MRI will not be considered accrued on this study. The optimized DWI images will be acquired on a dedicated research Siemens 3T Scanner belonging to Washington University's Center for Clinical Imaging Research. The standard-of-care FDG PET/CT mages will be acquired at one of the Siemens Biograph clinical PET/CT units located throughout the Barnes-Jewish Hospital Systems. We will compare the ADC values (ADCmin and ADCmean) to the optimized DWI sequence to FDG PET

SUVmax. For up to 1 year post-treatment, patients' medical records will be reviewed after scheduled SOC visits to additionally assess for clinical outcomes.

	Baseline	up to 3 Weeks Post-Treatment	3-6 Months Post-Treatment	Follow up for up to 1 year post-treatment
Screening	X			
Enrollment	X			
Medical Record Review	X	X	X	X
DWI MRI		X		
FDG PET/CT			SOC	

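### Section 7.0 makes PET SUVmax both the reference standard and the comparator, so the primary DWI-minus-PET difference is 0 at best, and this conflicts with the Section 2.0 gold standard

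*Combined protocol and SAP*

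**What the plan says.** All references are to the combined protocol and SAP.

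- **Section 7.0, Study Design and Endpoints.** The design is paired. The primary endpoints of sensitivity and specificity "will evaluate the diagnostic accuracy of the optimized DWI sequence ADCmean/min versus the standard-of-care FDG PET/CT SUVmax". PET is therefore one of two tests being evaluated.
- **Section 7.0, Aim 1.** "FDG-PET SUVmax results will be used as the reference standard for tumor or non-tumor tissue". PET is therefore also the truth.
- **Section 7.0, later in the same analysis text.** "A 90% confidence interval will be calculated for the differences in sensitivity and specificity of the enhanced DWI sequence ADCmean/min", with PET SUVmax as the comparator. This sentence names no reference standard.
- **Section 2.0, Objectives.** "The gold-standard will be histological tissue where available and/or 1-year clinical and imaging outcomes". The hypothesis in the same paragraph says that DWI will identify tumor "as confirmed by the clinical FDG PET/CT obtained at 3-6 months", which leans towards PET as the reference.
- **Section 1.0.** "Metabolic imaging with FDG PET/CT is impacted by false-positives in the setting of inflammation or post-radiation necrosis".
- **Section 4.0, Imaging Plan.** For up to 1 year after treatment, "medical records will be reviewed after scheduled SOC visits to additionally assess for clinical outcomes".

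Section 7.0 mentions neither histology nor 1-year outcome as a reference, and it does not point back to Section 2.0.

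**The concern.** A test cannot be compared for accuracy with its own reference. If tumor status is the PET call, PET cannot be wrong, and every discordant patient is booked as a DWI error. Errors that the two tests share are credited to DWI as correct. The plan itself expects PET errors, because Section 1.0 cites false positives from inflammation and necrosis.

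Both primary endpoints are affected. So are PPV, NPV, AUC and the Youden-selected ADC cut-off: under this reference they measure agreement with PET, not accuracy for tumor. A DWI sequence that is truly better than PET would be reported as worse. That could end a useful line of work or misdirect the study that follows this pilot.

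**Working it through.** **Plan's own figure.** There is none to reproduce. The sample size of 60 is justified by feasibility, and Section 7.0 disclaims a power calculation.

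**Step 1: the identity (no assumptions about accuracy).** Let the reference be the PET call, with one SUVmax cut-off in both roles.

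- PET sensitivity = P(PET+ | PET+) = 1. PET specificity = P(PET− | PET−) = 1.
- Difference in sensitivity = DWI sensitivity − 1 ≤ 0. Difference in specificity = DWI specificity − 1 ≤ 0.
- Zero is reached only with complete agreement. For example, DWI at 0.90/0.90 against PET gives −0.10/−0.10.

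**Step 2: could different cut-offs rescue it?** The PET/CT processing section cites literature values (above 9.0 for the primary mass, above 4.5 for nodes) but fixes no analysis cut-off. If two cut-offs were used for one lesion type, the PET-positive sets would be nested. One PET measure would stay at 100%, and the other could fall below 100%, so that one difference could favour DWI. No such plan is written.

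**Step 3: perfect DWI (illustration).** Prevalence π and PET accuracy are assumed; the documents give neither. If DWI equals the truth, its apparent sensitivity is PET's PPV and its apparent specificity is PET's NPV. With PET at 80%/85%:

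| π | Apparent sensitivity | Apparent specificity |
|---|---|---|
| 0.2 | 0.160/0.280 = 57% | 0.680/0.720 = 94% |
| 0.3 | 0.240/0.345 = 70% | 0.595/0.655 = 91% |
| 0.4 | 0.320/0.410 = 78% | 0.510/0.590 = 86% |

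At π = 0.3, PET errors are 0.3 × 0.20 + 0.7 × 0.15 = 0.165, or 9.9 of 60 patients. All of them would be scored as DWI errors.

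A more accurate PET shrinks the distortion. At π = 0.3, PET 90%/90% gives 0.27/0.34 = 79% and 0.63/0.66 = 95%. PET 95%/95% gives 0.285/0.320 = 89% and 0.665/0.680 = 98%.

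**Step 4: imperfect DWI with correlated errors (illustration).** Write Sp, Cp for PET sensitivity and specificity, Sd, Cd for DWI, and f for the share of the maximum positive error covariance.

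- a11 = Sp·Sd + f·(min(Sp, Sd) − Sp·Sd); a00 = 1 − Sp − Sd + a11
- b11 = (1−Cp)(1−Cd) + f·(min(1−Cp, 1−Cd) − (1−Cp)(1−Cd)); b00 = Cp + Cd − 1 + b11
- Apparent sensitivity = [π·a11 + (1−π)·b11] / [π·Sp + (1−π)(1−Cp)]
- Apparent specificity = [π·a00 + (1−π)·b00] / [π(1−Sp) + (1−π)·Cp]

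Take PET 80%/85%, DWI 90%/90% and π = 0.3. The true difference is +10/+5 points.

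| f | Apparent DWI sensitivity | Apparent DWI specificity | Reported difference (points) |
|---|---|---|---|
| 0 | 0.2265/0.345 = 0.657 | 0.5415/0.655 = 0.827 | −34/−17 |
| 0.5 | 0.26825/0.345 = 0.778 | 0.58325/0.655 = 0.890 | −22/−11 |
| 1 | 0.310/0.345 = 0.899 | 0.625/0.655 = 0.954 | −10/−5 |

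At f = 1 the error correlations are 0.67 in diseased and 0.79 in non-diseased patients. At π = 0.2 the reported differences are −44/−14 (f = 0) and −14/−3 (f = 1). At π = 0.4 they are −28/−21 and −7/−7. The negative sign follows from step 1; these figures show only the size.

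**Step 5: what an independent reference would give (illustration).** The difference can then take either sign. Assume 20–40% of 60 recur, DWI is 0.90 or 0.95 on both measures with PET 0.10 lower, and errors are independent. The 90% half-width is 1.645 × √{[a(1−b) + b(1−a) − (a−b)²]/n}, where a and b are the two proportions. For sensitivity it runs from 0.14 (0.95 v 0.85, n = 24) to 0.24 (0.90 v 0.80, n = 12). For specificity it runs from 0.10 (0.95 v 0.85, n = 48) to 0.14 (0.90 v 0.80, n = 36).

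**The case against.** The strongest reply is that the reference sentence sits directly before the ADC distributions, t-test and ROC analysis, where it sensibly defines the two tissue groups. The confidence-interval sentence names no reference. Read with Section 2.0 and the planned 1-year follow-up, the paired comparison could be meant against histology and outcome, and it would then not be degenerate. This reading is possible, but Section 7.0 neither says it nor refers back to Section 2.0. Even then, the Youden ADC cut-off would be tuned to PET and then judged against a different truth.

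A second reply is that PET as reference is partly the intended design, given the hypothesis wording in Section 2.0. This stands to a degree: an analysis of ADC against SUVmax agreement is coherent in a pilot. It does not rescue the DWI-minus-PET difference, which is the stated primary comparison. Pilot status explains the lack of a power calculation, but not a comparison whose sign is set in advance.

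It is also fair to say that the illustrative sizes rest on assumed PET accuracy, and that DWI is modelled at fixed accuracy although the plan selects its threshold from the study data. The identity does not depend on either.

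**Conclusion.** The concern holds and must be fixed before analysis. Under Section 7.0 as written, PET is perfect by construction and the primary difference cannot exceed 0. This rests on two conditions: that the Aim 1 reference sentence governs the paired comparison, and that one SUVmax cut-off serves both roles. The plan writes no alternative to either. If the first condition is dropped, the reference for the primary comparison is simply unstated in Section 7.0 and contested within Section 2.0. The size of the distortion is not known from the documents; the illustrations show that it could exceed the true difference and reverse its sign.

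**What to change.** In Section 7.0, define tumor status for both tests by the Section 2.0 gold standard: histology where obtained, otherwise 1-year clinical and imaging outcome. The prespecified rule should:

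- exclude the study 3–6 month SUVmax, including any PERCIST assessment based on that scan (this narrows the Section 2.0 list and should be said openly);
- state the time window in which a recurrence after the MRI counts as positive;
- state how patients without recurrence and with less than 1 year of follow-up are handled, for example as indeterminate, with sensitivity analyses counting them all positive and then all negative.

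Score DWI and PET separately against that status and give a paired 90% confidence interval for each difference. Keep ADC versus SUVmax as a descriptive agreement analysis, and reconcile the hypothesis wording in Section 2.0. If the sponsor prefers PET as the reference, the coherent alternative is to drop the difference and restate the primary endpoints as agreement with PET, which gives up the comparative-accuracy question.

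**Cost.** No new procedures are needed. Section 4.0 already lists biopsy, pathology-confirmed recurrence, recurrence date and last clinical and imaging follow-up, and plans record review for up to 1 year. The primary analysis must wait for those outcomes, and the assignment rule must be written. The visible data list has no RECIST, PERCIST or iRECIST field, so the sponsor should confirm that the data sheet supports the rule for patients without biopsy. One limitation remains and should be stated: "PET/CT studies are standard of care and are reported as clinical studies", so biopsy decisions and charted outcomes may still partly reflect the PET result.
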